6.6.2 Recommended treatment of adverse events

At present there is insufficient information to provide specific recommendations regarding treatment of adverse events. Should a subject have an incidental and limited need for a medication to be taken within the restricted pre-dose timeframe (e.g., ibuprofen for a headache, antibiotic prophylaxis prior to dental surgery, etc.), the sponsor should be advised, as administration of any concomitant medication may require the subject to be withdrawn.

Medication used to treat AEs must be recorded on the Concomitant Medications/Significant non-drug therapies CRF.

6.6.3 Emergency breaking of assigned treatment code

Emergency breaking of the assigned treatment code must only be undertaken when it is essential to treat the subject safely and efficaciously. Most often, study treatment discontinuation and knowledge of the possible treatment assignments are sufficient to treat a study subject who presents with an emergency condition. A complete sets of emergency code break cards is provided to Novartis - to be distributed to the investigators. All code break cards must be retained until the end of the study and returned to Novartis. They must be stored in a secure place but be accessible in case of emergency. The investigator will receive a code break card for each subject, with the details of study treatment covered by a removable, scratch-off cover. In an emergency, the scratch-off cover can be removed to determine the treatment. The scratch-off covers are not to be removed for any reason other than an emergency. When the investigator removes the scratch-off cover he/she must note the date, time, and reason for removing it and retain this information with the case report form documentation. The assigned treatment must not be recorded on the CRF. The investigator must also immediately inform the Novartis local monitor that the code has been broken.

It is the investigator's responsibility to ensure that there is a dependable procedure in place to allow access to the code break cards at any time in case of emergency. The investigator will provide:

- protocol number
- name
- subject number

In addition, oral and written information to the subject must be provided on how to contact his/her backup in cases of emergency, or when he/she is unavailable, to ensure that un-blinding can be performed at any time.

Where possible, subjects should continue with the follow-up visit as per Assessment Schedule (Table 8-1 and Table 8-2) after code break.

6.7 Preparation and dispensation

Each study site will be supplied with study drug in packaging as described under the investigational and control drugs section (Section 6.1.1).

KAE609 will be administered to the subject at the study center via the following route of administration:

- iv bolus administration over approximately 2 min (cohorts A1, A2 and B1)
- iv infusion over approximately 10 min (cohorts A3, A4, A5 and B2)

Depending on emerging data of this study infusion duration might be adapted (for example infusion over 10 min instead of bolus injection).

See the SOM and Pharmacy Manual for further details.

7 Informed consent procedures

Eligible subjects may only be included in the study after providing (witnessed, where required by law or regulation), IRB/IEC-approved informed consent.

Informed consent must be obtained before conducting any study-specific procedures (e.g. all of the procedures described in the protocol). The process of obtaining informed consent must be documented in the subject source documents.

Novartis will review the investigators/CRO proposed informed consent form to ensure it complies with the ICH E6 GCP guidelines and regulatory requirements and is considered appropriate for this study. Any further changes to the proposed consent form suggested by the investigator must be agreed to by Novartis before submission to the IRB/IEC.

Information about common side effects already known about the investigational drug can be found in the Investigator's Brochure. This information will be included in the subject informed consent and should be discussed with the subject during the study as needed. Any new information regarding the safety profile of the investigational drug that is identified between Investigator's Brochure updates will be communicated as appropriate, for example, via an investigator notification or an aggregate safety finding. New information might require an update to the informed consent and then must be discussed with the subject.

Male subjects must be informed that if a female partner becomes pregnant while he is enrolled in the study, contact with the female partner will be attempted to request her consent to collect pregnancy outcome information.

Commercially Confidential Information

A copy of the approved version of all consent forms must be provided to Novartis/sponsor after IRB/IEC approval.

Refer to the SOM for a complete list of ICFs included in this study.

8 Visit schedule and assessments

Assessment schedule lists all of the assessments and indicates with an “X”, the visits when they are performed. All data obtained from these assessments must be supported in the subject’s source documentation.

Subjects should be seen for all visits/assessments as outlined in the assessment schedule or as close to the designated day/time as possible. Missed or rescheduled visits should not lead to automatic discontinuation. Subjects who prematurely discontinue the study for any reason should be scheduled for a visit as soon as possible, at which time all of the assessments listed for the EOS visit will be performed. At this EOS visit, the adverse event and concomitant medications should be recorded on the CRF.

Specification and timing of each assessment are detailed in the protocol. The methods and recording of each assessment may be outlined in the SOM.

Epoch	Screening		Treatment Period										Post-Treatment Follow-Up					Post Study	
Visit Name	Screening	Baseline	Treatment										Follow-up				EOS	Safety Contact	
Days	-29 to -2	-1	1										2	3	4	6	8	30	
Time (post-dose)	-	-	-1h ¹	0h	2min ²	10min	30min	1h	3h	4h	6h	12h	24h	48h	72h	120h	-	-	
12 lead Holter continuous ECG ⁸			X																
ECG evaluation ⁴	X	X	X			X	X	X	X		X	X	X				X		
Blood Pressure and Pulse Rate	X	X	X			X	X	X	X				X		X		X		
Drug administration record ⁷				X															
Injection/infusion site observation			X		X		X												
Blood chemistry	X	X											X		X		X		
Hematology	X	X											X		X		X		
Urinalysis	X	X											X				X		
PK blood collection			X		X	X	X	X	X		X	X	X	X	X	X	X		
CCI			X																
CCI			X																
Inpatient			X																
Concomitant medications	X ¹⁰																		
Adverse events/serious adverse events	X ¹⁰																		

Epoch	Screening		Treatment Period										Post-Treatment Follow-Up					Post Study	
Visit Name	Screening	Baseline	Treatment										Follow-up				EOS	Safety Contact	
Days	-29 to -2	-1	1										2	3	4	6	8	30	
Time (post-dose)	-	-	-1h ¹	0h	2min ²	10min	30min	1h	3h	4h	6h	12h	24h	48h	72h	120h	-	-	
Study completion information																		X	
Safety Follow up Call																			S

^X Assessment to be recorded in the clinical database or received electronically from a vendor

^S Assessment to be recorded in the source documentation only

¹ Pre-dose

² Only collected/done in cohorts with bolus injection.

³ Serum pregnancy test at screening and EOS visit. Urine pregnancy test at baseline. FSH testing at screening.

⁴ 12 lead ECG. Triplicate measurements are required at Screening, Baseline and EOS and single ECG measurements at other timepoints.

Commercially Confidential Information

¹⁰AEs and concomitant medications will be captured in the eCRF through post study safety-follow up call

^X Assessment to be recorded in the clinical database or received electronically from a vendor

^S Assessment to be recorded in the source documentation only

¹ Pre-dose

² Only collected/done in cohorts with bolus injection.

³ Serum pregnancy test at screening and EOS visit. Urine pregnancy test at baseline. FSH testing at screening.

⁴ 12 lead ECG. Triplicate measurements are required at Screening, Baseline, day 3, day 4 and EOS and single ECG measurements at other timepoints.

Commercially Confidential Information

⁹ AEs and concomitant medications will be captured in the eCRF through post study safety-follow up call

8.1 Screening

It is permissible to re-screen a subject once if s/he fails the initial screening or was not randomized in the required timeframe. Subjects need to re-consented for re-screening and a new subject number must be assigned.

In the case where a safety laboratory assessment at screening and/or baseline is outside of the range specified in the exclusion criteria, the assessment may be repeated once at screening and once at randomization. If the repeat value remains outside of the specified ranges, the subject must be excluded from the study.

8.1.1 Eligibility screening

Results of below screening measurements will be available as source data at the study site and will not be recorded within the eCRF.

Commercially Confidential Information

8.1.2 Information to be collected on screening failures

Information on what data must be collected for screening failures and further information on re-screening is outlined in the SOM.

8.2 Subject demographics/other baseline characteristics

Subject demographic and baseline characteristic data will be collected on all subjects. Subject demographics include date (if permitted) or year of birth, sex, race and predominant ethnicity (if permitted). Relevant medical history/current medical conditions data will also be collected until signature of informed consent. Where possible, the diagnoses and not symptoms should be recorded.

All prescription medications, over-the-counter drugs and significant non-drug therapies prior to the start of the study must be documented. See the [Section 6.2.1](#) for further details on what information must be recorded on the appropriate page of the eCRF.

8.3 Efficacy

Efficacy / Pharmacodynamics are not measured in this study.

8.3.1 Appropriateness of efficacy assessments

Efficacy / Pharmacodynamics are not measured in this study.

8.4 Safety/Tolerability

Safety assessments are specified in the Assessment Schedule ([Table 8-1](#) and [Table 8-2](#)) which details when each assessment is to be performed.

For details on AE collection and reporting, refer to [Section 10.1](#).

Table 8-3 Assessments and Specifications

Assessment	Specification
Physical examination	
A complete physical examination at screening will include the examination of general appearance, skin, neck (including thyroid), eyes, ears, nose, throat, lungs, heart, abdomen, back, lymph nodes, extremities, vascular, and neurological. If indicated based on medical history and/or symptoms, rectal, external genitalia, breast, and pelvic exams will be performed.
 
At other visits, a shorter physical exam may be performed to include the examination of general appearance.
 
Information for all physical examinations must be included in the source documentation at the study site. Clinically relevant findings that are present prior to signing informed consent must be included in the Medical History part of the CRF. Significant findings made after signing informed consent which meet the definition of an Adverse Event must be recorded on the Adverse Event section of the CRF.

Injection/infusion site observation	
Injection/infusion site must be examined before and after drug administration for any changes in appearance or pain.
 
Local tolerability at the injection/infusion site will be assessed by the investigator prior and immediately after each infusion on day 1 (Part A and B) and 5 (Part B only).
 
The following parameters will be evaluated by scoring (none, mild, moderate or severe) in each subject:
 
 • Pain • Itching • Erythema • Swelling • Inflammation • Phlebitis • Ulceration • Necrosis 
Infusion reactions also need to be captured as AE according to CTCAE criteria.

Assessment	Specification
Blood pressure and pulse rate	Systolic and diastolic blood pressure will be measured after the subject has been supine for five minutes, using an automated validated device with an appropriately sized cuff. In case the cuff sizes available are not large enough for the patient's arm circumference, a sphygmomanometer with an appropriately sized cuff may be used.
Body temperature	Oral body temperature will be recorded in °C.
Height and weight	Height in centimeters (cm) and body weight (to the nearest 0.1 kilogram (kg) in indoor clothing, but without shoes) will be measured.

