1.2 Purpose

The purpose of this study is to assess the safety and tolerability and pharmacokinetics (PK) of single ascending doses (SAD) and multiple ascending doses (MAD) of KAE609 administered by iv infusion in healthy subjects, to support further clinical development of KAE609 in patients with severe malaria and to guide dose selection for future trials.

2 Objectives and endpoints

Table 2-1 Objectives and related endpoints

Objective(s)	Endpoint(s)
Primary objective(s)	Endpoint(s) for primary objective(s)

 To assess the safety and tolerability of single and multiple iv doses of KAE609 in healthy subjects 	
 Adverse events, physical examination findings, vital signs, ECG findings (including QTcF), safety laboratory assessments including chemistry, hematology, and urinalysis results
Secondary objective(s)	Endpoint(s) for secondary objective(s)

 To assess the pharmacokinetics (PK) of single and multiple iv doses of KAE609 in healthy subjects 	
 AUC, Tmax, Cmax, CL, Vz, and T1/2

 To assess local tolerance at infusion site of KAE609 iv administration 	
 Findings of physical examination of infusion site

Commercially Confidential Information

3 Study design

This is a randomized, subject and investigator-blinded, placebo-controlled, single and multiple ascending iv dose study in healthy subjects. The study consists of two parts and the study scheme is shown in [Figure 3-1](#):

- Part A is a single ascending dose (SAD) study with 5 cohorts of 8 subjects each
- Part B is a multiple ascending dose (MAD) study with 2 cohorts of 9 subjects each

For both parts of the study, each subject will participate in an up to 28- day screening period during which a full physical examination, medical history, drug screening, vital signs, ECG evaluation and safety laboratory tests evaluation will be performed.

A review of safety and PK data will be conducted at the completion of each cohort prior to dosing of the next subsequent cohort. Please also refer to [Section 6.5.1](#) for more details on dose escalations. Safety assessments will include physical examinations, ECGs, vital signs, standard clinical laboratory evaluations (hematology, blood chemistry, urinalysis) adverse event and serious adverse event monitoring.

Commercially Confidential Information

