Part A: Single-ascending dose study

In Part A sequential cohorts of 8 healthy subjects per cohort will be randomized to receive successively higher single iv doses of KAE609 or matching placebo. In each cohort, subjects will be randomized in a 3:1 ratio to KAE609 (6 subjects/cohort) or matching placebo (2 subjects/cohort). Five planned dose cohorts will be included in Part A (A1, A2, A3, A4 and A5). Provisional dose levels are described in [Section 6.5.1.2](#).

Commercially Confidential Information

For a detailed outline of safety and other assessments, please refer to Part A Assessment Schedule ([Table 8-1](#)). If added, any additional dose cohort will follow the same Part A [Assessment Schedule](#).

Figure 3-2 Study design - SAD

Commercially Confidential Information

Part B: Multiple-ascending dose study

In Part B sequential cohorts of 9 healthy subjects per cohort will be randomized to receive successively higher iv doses of KAE609 or matching placebo. Two planned dose cohorts will be included in Part B (B1 and B2). For Cohort B1, healthy subjects will receive a 60 mg dose of KAE609 or matching placebo iv q24h for 5 days. For Cohort B2, healthy subjects will receive a 120 mg dose of KAE609 or matching placebo iv q24h for 5 days. In each cohort, subjects will be randomized in a 2:1 ratio to KAE609 (6 subjects/cohort) or matching placebo (3 subjects/cohort). Provisional dose levels are described in [Section 6.5.1.2](#)

Commercially Confidential Information

For a detailed outline of safety and other assessments, please refer to Part B Assessment Schedule ([Table 8-2](#)). Any additional cohort will follow the same Part B [Assessment Schedule](#).

Figure 3-3 Study design - MAD

Commercially Confidential Information

4 Rationale

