10.1 Definition of adverse events and reporting requirements

10.1.1 Adverse events

An adverse event (AE) is any untoward medical occurrence (e.g., any unfavorable and unintended sign [including abnormal laboratory findings], symptom or disease) in a subject or clinical investigation subject after providing written informed consent for participation in the study. Therefore, an AE may or may not be temporally or causally associated with the use of a medicinal (investigational) product.

The investigator has the responsibility for managing the safety of individual subject and identifying adverse events.

Novartis qualified medical personnel will be readily available to advise on trial related medical questions or problems.

The occurrence of adverse events must be sought by non-directive questioning of the subject at each visit during the study. Adverse events also may be detected when they are volunteered by the subject during or between visits or through physical examination findings, laboratory test findings, or other assessments.

Adverse events must be recorded in the Adverse Events CRF under the signs, symptoms or diagnosis associated with them, accompanied by the following information (as far as possible) (if the event is serious refer to [Section 10.1.2](#)):

1. The Common Toxicity Criteria (CTC) AE grade (version 5 or higher)
 - Adverse events will be assessed and graded according to the Common Terminology Criteria for Adverse Events (CTCAE)
 - If CTCAE grading does not exist for an adverse event, use 1=mild; 2=moderate, 3=severe; and 4=life threatening. CTCAE grade 5 (death) is not used, but is collected in other CRFs (e.g., End of Study Visit, Death/Survival).
2. its relationship to the study treatment
3. its duration (start and end dates) or if the event is ongoing, an outcome of not recovered/not resolved must be reported.
4. whether it constitutes a SAE (see [Section 10.1.2](#) for definition of SAE) and which seriousness criteria have been met
5. action taken regarding with study treatment.

All adverse events must be treated appropriately. Treatment may include one or more of the following:

- No treatment given
 - Dose not changed
 - Dose Reduced/increased
 - Drug interrupted/withdrawn
6. its outcome
 - a. not recovered/not resolved;
 - b. recovered/resolved;
 - c. recovering/resolving,
 - d. recovered/resolved with sequelae;
 - e. fatal;
 - f. or unknown.

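### In Part A the infusion-site score has no scheduled look later than 30 minutes after dosing, so delayed local signs can miss the local tolerance summary

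*Protocol*

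**What the plan says.** Protocol Table 2-1 lists as a secondary objective "To assess local tolerance at infusion site of KAE609 iv administration", with the endpoint "Findings of physical examination of infusion site".

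Table 8-3 (section 8.4) gives the method. Pain, itching, erythema, swelling, inflammation, phlebitis, ulceration and necrosis are each scored none, mild, moderate or severe. Local tolerability is "assessed by the investigator prior and immediately after each infusion on day 1" in Parts A and B, and likewise on Day 5 in Part B only. Infusion reactions must also be recorded as adverse events with a CTCAE grade.

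In the Part A schedule (Table 8-1), the row "Injection/infusion site observation" is marked, by column position, at 1 h pre-dose, 2 min and 30 min. The 2 min column carries the footnote "Only collected/done in cohorts with bolus injection". Nothing is marked from 1 h to Day 8.

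For analysis, SAP 7.2 has one sentence: local tolerance is summarised by part and treatment group. Protocol 12.4.2 makes a separate table of infusion-site-reaction adverse events optional.

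**The concern.** Some of the eight signs, such as pain and itching, can be present at once. Others, such as phlebitis, ulceration and necrosis, may take longer to show. If a sign appears after the last scored look, the score records none for that subject whatever happens later.

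Protocol 4.5 says that there is no clinical experience with the iv form, and section 1.2 says that the study is to guide dose selection. Local tolerance is the question most specific to the new route. A score table with no delayed signs could be read as reassurance about a period in which no site was scored. The comparison with placebo on those signs would then rest on adverse event reports rather than on blinded inspection at fixed times.

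**Working it through.** **When the site is scored**

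- Part A, bolus cohorts (A1 and A2, section 6.7): pre-dose, 2 min, 30 min.
- Part A, infusion cohorts (A3 to A5): pre-dose and 30 min.
- Part A visits with no score: 24, 48, 72 and 120 h, and EOS on Day 8. PK blood is drawn at all of them.
- Part B: before and immediately after the dose on Days 1 and 5. Dosing is daily (for B1, "60 mg dose of KAE609 or matching placebo iv q24h for 5 days"; B2 has the same pattern). The Day 5 pre-dose score therefore falls 4 × 24 = 96 h after dose 1 and 24 h after dose 4. It is a delayed look at doses 1 to 4. The documents do not say whether the same vein is used. Nothing is described after the Day 5 post-dose look.

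**The plan's own detection figure**

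Section 12.8.1 and Table 12-2 use 6 active subjects per cohort. At a true rate p = 0.2:

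- no event: 0.8^6 = 26.2% (stated 26%)
- at least one: 1 − 0.8^6 = 73.8% (stated 74%)
- at least two: 1 − 0.8^6 − 6 × 0.2 × 0.8^5 = 34.5% (34.46% before rounding; stated 34%)

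All 15 cells of the table reproduce. The figures assume that an event which occurs is observed.

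**The same figure for the score**

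Let f be the share of true site reactions visible at the last scored look. The documents give no value, so f is an assumption and is shown as a range. The chance that the score records at least one event among n active subjects is 1 − (1 − p·f)^n. For example, at p = 0.2 and f = 0.25 with n = 6, it is 1 − 0.95^6 = 26%.

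| f | p = 1 in 5, n = 6 | p = 1 in 10, n = 6 | p = 1 in 5, n = 30 |
|---|---|---|---|
| 1 | 74% | 47% | 99.9% |
| 0.5 | 47% | 26% | 95.8% |
| 0.25 | 26% | 14% | 78.5% |
| 0.1 | 11% | 6% | 45.5% |
| 0 | 0% | 0% | 0% |

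The n = 30 column pools all active Part A subjects (5 cohorts × 6) and assumes one rate at every dose. The row f = 1 is the ceiling: later looks that miss nothing.

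**Whether another route feeds the endpoint**

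- Physical examination: Table 8-3 allows a shorter examination after screening that covers general appearance. The infusion site is not named.
- Adverse events: "The occurrence of adverse events must be sought by non-directive questioning of the subject at each visit during the study". Section 10.1.1 adds that events may be volunteered or found on examination. Monitoring continues for at least 30 days after the last dose.
- Reporting: adverse events are tabulated by system organ class, preferred term and treatment (protocol 12.4.2, SAP 7.2). Neither document counts infusion-site events towards local tolerance.

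**The case against.** The strongest reply is that late reactions are not lost. Infusion reactions must be recorded as adverse events, subjects are domiciled after dosing for observation (section 4.1), and the standard adverse event tables by treatment are mandatory. Grade 3 or higher injection site reactions in two or more subjects also trigger a pause (section 9.1.4). All of this stands. A reader might infer that late local harm would go unseen, or that KAE609 could not be compared with placebo on it. The documents do not support either reading. The gap is in the scored secondary endpoint, not in safety monitoring.

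A reader might also infer that the score is bound to be none for phlebitis, ulceration and necrosis because these cannot develop in time. That needs f close to 0, and neither document gives onset times. At f = 0.25 and a rate of 1 in 5, the 30 active Part A subjects would still give a 78.5% chance of at least one scored event. Nor does that reading fit Part B, where 12 of the 42 planned active subjects have the Day 5 pre-dose look at earlier doses.

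Two limits of the text also count. Table 8-2 is not available here, so further Part B looks cannot be excluded. The visible part of Table 8-1 has no physical-examination row, and the endpoint is worded as examination findings, not expressly as the eight-sign score. Even so, the eight-sign score is the only site assessment that the plan specifies, and later examinations need not include the site.

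Finally, the analysis is descriptive with no hypothesis on local tolerance. That limits the consequence but does not supply the missing look.

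**Conclusion.** The point holds in a limited form. In Part A no eight-sign score is scheduled later than 30 minutes after dosing. In Part B none is described after the Day 5 post-dose look, which cannot be confirmed without Table 8-2. Delayed signs reach the study as adverse events that are not stated to be part of the local tolerance summary, so a clean score table could overstate tolerance for those signs.

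The size depends on f. For one cohort at a true rate of 1 in 5, detection by the score falls from 74% to 47%, 26% or 11% as f goes from 1 to 0.5, 0.25 or 0.1. This assumes independent subjects and that every visible sign is scored. The change is worth making because the visits already exist. The gap does not undermine the primary safety objective.

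**What to change.** 1. In Table 8-3 and Table 8-1, repeat the same eight-sign score of the used site at 24 h, 72 h and EOS in Part A.
2. In the Part B schedule, add the score about 24 h after the last dose, if a visit exists, and at EOS. Section 8.4.3 runs the Day 5 Holter recording to 24 h post-dose, which suggests contact at that time. Record whether the access site changed between doses.
3. In SAP 7.2, summarise the worst post-dose score per subject and sign by treatment. Make the table of infusion-site adverse events by treatment a required part of the local tolerance summary.
4. Reconcile the post-dose timing: Table 8-3 says immediately after dosing, while Table 8-1 marks only 30 min for the infusion cohorts.

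The cost is a brief inspection at visits that already take place, a few more CRF entries and a schedule amendment. The small downside is some minor cannula-related findings in both arms, which the placebo group helps to interpret. If the schedule cannot be changed, item 3 can still be done for the adverse events and would make the limits of the score plain.
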